## **8.2 Populations for Analyses**

The following participant populations will be used in the study:

- All enrolled participants: All participants who signed an ICF and were registered into the IVRS;
- All treated participants: All participants who received at least one dose of study medication;
- Pharmacokinetic Population: All participants who received any study drug and have available concentration time data;
- Immunogenicity Population: All participants who received any study drug and have at least one post treatment immunogenicity measurement;
- Biomarker Population: All MSI-H/dMMR CRC centrally confirmed participants who received any study drug unless otherwise stated

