#### **1.3.3    Exploratory Objectives**

The exploratory objective for Part 1 is:

- To assess preliminary anti-tumor activity of nivolumab and ipilimumab in Chinese participants when administered in combination.

The exploratory objectives for Part 2 are:

Per Protocol Amendment 07, collection of PK and immunogenicity data is not applicable. PK sample analyses and immunogenicity assessments will be based on samples collected before the implementation of protocol amendment 07. No analyses of concordance rate between results from central and local testing and the investigator-assessed second disease progression or death during next line of treatment are planned due to the limited number of participants enrolled.

- To determine the safety and tolerability (defined as toxicity rates [worst Common Terminology Criteria (CTC) Grade per participant]) of AEs and specific laboratory tests of nivolumab in combination with ipilimumab in Chinese participants with recurrent or metastatic MSI-H/dMMR CRC.
- To characterize the PK of nivolumab and ipilimumab when administered in combination, and to explore exposure-response relationships.
- To characterize the immunogenicity of nivolumab and ipilimumab when administered in combination.
- To evaluate health-related quality of life using a validated instrument in the European Organisation for Research and Treatment of Care (EORTC) Quality of Life Questionnaire Core-30 (QLQ-C30).
- To evaluate subject-reported general health status as assessed by the EQ-5D-3L questionnaire.
- To evaluate overall survival (OS) in Chinese participants with recurrent or metastatic MSI-H/dMMR CRC who received nivolumab in combination with ipilimumab.

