### 3 INVESTIGATIONAL PLAN

#### 3.1 Study Design and Duration

##### 3.1.1 Overall Design and Schematic

This is an open-label, multi-dose, 2-part, Phase 1/2 study of nivolumab in combination with ipilimumab in Chinese participants with previously treated metastatic or recurrent solid tumors.

As of 20-Dec-2021, the study was closed to new enrollment for Part 2, and a total of 36 participants (9 participants each in Arms A, B, C, and D) were treated in the 3 nivolumab/ipilimumab combination dosing regimens as described below and in Table 3.1.1-1. For all arms, treatment was not randomized.

In Part 1, 9 participants were treated in each of the three arms:

- **Arm A:** Nivolumab administered IV over 30 minutes at 3 mg/kg every 2 weeks combined with ipilimumab administered IV over 30 minutes at 1 mg/kg every 6 weeks
- **Arm B:** Nivolumab administered IV over 30 minutes at 3 mg/kg combined with ipilimumab administered IV over 30 minutes at 1 mg/kg every 3 weeks for 4 doses followed by nivolumab administered IV over 30 minutes at 240 mg every 2 weeks
- **Arm C:** Nivolumab administered IV over 30 minutes at 1 mg/kg combined with ipilimumab administered IV over 30 minutes at 3 mg/kg every 3 weeks for 4 doses followed by nivolumab administered IV over 30 minutes at 240 mg every 2 weeks

In Part 2, a total of 9 participants with recurrent or metastatic MSI-H/dMMR CRC determined by local testing were treated in the following treatment arm:

- **Arm D:** Nivolumab administered IV over 30 minutes at 3 mg/kg combined with ipilimumab administered IV over 30 minutes at 1 mg/kg every 3 weeks for four doses followed by nivolumab administered IV over 30 minutes at 240 mg every 2 weeks.

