#### **3.1.3.2 Screening**

A complete schedule of activities for screening can be found in [Table 5.1-1](#).

Before Protocol Amendment 07, enrollment had stopped.

- Begins by establishing the participant's initial eligibility and signing of the informed consent form (ICF).
- Inclusion/Exclusion criteria are assessed during the screening period and must be confirmed prior to first dose
- All medical history relevant to the disease under study should be collected.
- Tumor tissue obtained from primary or metastatic site of disease.
  - Sufficient tumor tissue obtained before start of study treatment in the primary or metastatic sites (block or minimum of 10 slides, obtained from core biopsy, punch biopsy, excisional biopsy, or surgical specimen) will be submitted to the central laboratory.
  - For participants where a fresh biopsy is not feasible, archival tumor material are required.
  - An additional source of tumor tissue must be available if the tissue obtained adhering to the above guidelines cannot be tested due to poor quality or insufficient quantity.
  - Central lab must confirm receipt of evaluable tumor tissue prior to vial assignment for MSI/MMR testing (see [Section 5.6.2](#)).
- Prior to screening, medical record documentation of MSI/MMR testing results must be available. Related pathology reports must be available. Reports must contain MSI/MMR status results, and specific results per markers tested for MSI/MMR are also required if available.
- Collect RAS and BRAF mutation status, if available. Tests for these alterations are expected to be already performed for Arm D participants.
- Eligibility and baseline assessments should be performed within required timeframe according to [Table 5.1-1](#). The screening phase either ends with confirmation of full eligibility and treatment assignment for the participant or with the confirmation that the participant is a screen failure.

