### **5.6.2 Part 2**

Tumor biopsy specimens will be obtained from consenting participants prior to treatment with nivolumab combined with ipilimumab to confirm MSI/MMR status in central lab.

Fresh biopsies is preferred for biomarker analysis if accessible and deemed safe by the investigator. The fresh biopsies submitted to central lab must be the same tissue sample as was used for local MSI/MMR testing.

If fresh biopsy cannot be obtained, archived tumor tissue (a block or 10 slides) prior to therapy is acceptable only if the archived tissue is the same tissue that was used for local MSI/MMR testing.

Central lab must confirm receipt of evaluable tumor tissue prior to vial assignment.

NOTE: Exceptions to above requirements need to be discussed with the medical monitor and will be handled in a case-by-case basis. An additional source of tumor tissue must be available if the tissue obtained adhering to the above guidelines can't be tested due to poor quality or quantity.

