#### **8.1.2 Part 2**

With an estimated discrepancy rate of 25% between local and repeating testing in central lab for MSI/MMR status, it is expected that approximately 33 participants with MSI-H/dMMR mCRC

determined by local testing will be treated in the study. A sample size of 33 will allow the lower bound of one-sided 95% CI excluding 35% when the observed ORR is 50% in the nivolumab/ipilimumab combination arm. The 35% ORR is expected for local diagnosed MSI-H/dMMR mCRC patients treated with PD-1 inhibitor monotherapy. This sample size will also provide at least 90% power to demonstrate statistical difference with historical ORR of 5% for TKI monotherapy in a similar setting at a two-sided alpha of 0.05.

Based on the estimated discrepancy rate between local and central MSI/MMR testing, of 33 treated participants, approximately 25 participants will have their MSI-H/dMMR status confirmed by repeating central lab testing. During the study, the discrepancy rate will be monitored in an ongoing basis, and study accrual may continue beyond 33 if the discrepancy rate exceeds 25%.

Due to challenges with enrollment, the enrollment for Part 2 was closed after 9 participants were treated, out of the 33 participants planned.

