### **8.4.2 Efficacy Analyses**

#### **8.4.2.1 Part 1**

Individual participant's BOR will be listed by arm and/or across arm based on RECIST 1.1. BOR outcomes will be tabulated by arm and/or across arms for all treated participants.

ORR will be calculated and corresponding two-sided 95% exact CIs using Clopper-Pearson method will be provided by arm and/or across arms for all treated participants.

PFS will be calculated by the Kaplan-Meier estimate for all treated participants.

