### **8.4.5 Biomarker Analyses**

Biomarker analyses are not applicable for Part 1 Arms A, B and C.

For Part 2 Arm D, baseline MSI/MMR status, both central and local testing, will be listed.

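### Does the unused Biomarker Population in section 8.2 mean that the Arm D MSI/MMR listing will leave out participants not confirmed centrally?

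*Combined protocol and SAP*

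**What the plan says.** Section 8.2 lists the populations to be used in the study. The last entry is "Biomarker Population: All MSI-H/dMMR CRC centrally confirmed participants who received any study drug unless otherwise stated".

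Section 8.4.5 rules out biomarker analyses for Part 1 and then gives a single instruction: "For Part 2 Arm D, baseline MSI/MMR status, both central and local testing, will be listed". Section 8.4.6 (exploratory biomarker analyses) is marked as not applicable.

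The related passages are these:

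- Section 3.1.1: in Part 2, "a total of 9 participants with recurrent or metastatic MSI-H/dMMR CRC determined by local testing were treated". Every Arm D participant is therefore MSI-H/dMMR by the local test.
- Section 5.6.2: tumor tissue is taken "prior to treatment with nivolumab combined with ipilimumab to confirm MSI/MMR status in central lab".
- Section 3.1.3.2: a second tissue source must be available if the first "cannot be tested due to poor quality or insufficient quantity".
- Section 8.1.2: of 33 planned participants, "approximately 25 participants will have their MSI-H/dMMR status confirmed by repeating central lab testing". Part 2 closed after 9 were treated.
- Section 1.3.3: "No analyses of concordance rate between results from central and local testing" are planned, because few participants were enrolled.
- Section 8.3.1.2: the denominator of the primary endpoint, BICR-assessed ORR, is the number of treated participants.

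**The concern.** A defined population that no analysis cites suggests that two parts of the plan have come apart. The PK and immunogenicity analyses do not name their populations either, so a programmer may match populations to sections by topic. Doing so would attach the Biomarker Population to the section titled Biomarker Analyses.

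That would defeat the listing. All 9 participants are MSI-H/dMMR locally, and the Biomarker Population keeps only those who are also MSI-H/dMMR centrally. Both columns would then be constant. A participant whom the central lab contradicted would be absent, and so would one with no evaluable central result, and the two could not be told apart. Participants were asked for tissue so that status could be confirmed centrally, and after Amendment 07 this listing is the only planned output of that testing.

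**Working it through.** **1. The plan's own figure.** Inputs from section 8.1.2: 33 planned participants and a 25% discrepancy rate. Expected number confirmed = 33 × (1 − 0.25) = 24.75, which the plan rounds to about 25. The figure reproduces.

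**2. Where could the Biomarker Population be used?**

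| Analysis | Section | Participants |
|---|---|---|
| BICR-assessed ORR | 8.3.1.2 | treated |
| Investigator-assessed ORR | 8.3.2.2 | all treated |
| Part 2 safety | 8.4.3 | all treated |
| QLQ-C30, EQ-5D-3L | 8.4.7.1, 8.4.7.2 | all treated |
| Concordance of local and central tests | 1.3.3 | not planned |
| Exploratory biomarkers | 8.4.6 | not applicable |
| MSI/MMR listing | 8.4.5 | Arm D |

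Only the last row could use it.

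**3. Which participants does the listing cover?** Two features of the text point the same way. The definition in 8.2 ends with a clause that yields to any different statement elsewhere, and 8.4.5 makes one by naming Arm D with no restriction to confirmed participants. Also, 8.4.5 calls for the central and the local result side by side, which is worthwhile only if they can differ. In the Biomarker Population they cannot. The natural reading is 9 treated participants and 9 rows.

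**4. What would the strained reading cost?** Let d be the chance that a participant is not confirmed centrally, taken as independent across the 9. Expected rows lost = 9d, and P(at least one lost) = 1 − (1 − d)^9.

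| d | Expected lost | P(at least one lost) |
|---|---|---|
| 5% | 0.45 | 0.370 |
| 10% | 0.90 | 0.613 |
| 25% (plan) | 2.25 | 0.925 |
| 40% | 3.60 | 0.990 |

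At d = 25%, the number lost lies between 0 and 4 with probability 0.951. The 5%, 10% and 40% rows are assumed values, since the observed discrepancy is not in the document. All of these losses arise only if step 3 is decided the other way.

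**5. Would a display of response by central status add anything?** Take invented counts: 5 responders among 9, with 2 participants unconfirmed. Clopper-Pearson two-sided 95% intervals:

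| Responders | Estimate | Interval | Width (points) |
|---|---|---|---|
| 5/9, all treated | 56% | 21.2% to 86.3% | 65.1 |
| 3/7 confirmed | 43% | 9.9% to 81.6% | 71.7 |
| 4/7 confirmed | 57% | 18.4% to 90.1% | 71.7 |
| 5/7 confirmed | 71% | 29.0% to 96.3% | 67.3 |

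Every interval among the confirmed is wider than the one for all treated. The display would describe a handful of individuals and would not sharpen the estimate.

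**The case for a change.** The best argument for acting is that matching populations to sections by topic is not far-fetched: it is the only way the PK and Immunogenicity Populations of 8.2 find a use. Naming an arm is also not quite the same as naming an analysis set. Amendment 07 edited both sections, removing the outcomes-research population from 8.2 and adding the listing to 8.4.5, so leaving this entry in place looks like an oversight. The correction would take a sentence and need no new data.

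Most of that is true as description. The label does look residual, and deleting it would do no harm. It does not follow that the listing is at risk. Topic matching has to override the exception clause in 8.2 and also empty the two-source comparison in 8.4.5 of content. A statistician preparing a nine-row listing of local against central status would notice that every row agreed by construction.

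The risk of missing central results is also smaller than it first looks. Besides requiring backup tissue, section 3.1.3.2 has the central lab confirm receipt of evaluable tissue before vial assignment. Section 5.6.2 allows case-by-case exceptions, so such results cannot be excluded.

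A further point is that Part 1 provides for each participant's "BOR will be listed by arm and/or across arm based on RECIST 1.1", while Part 2 plans no such listing. Confirmed responders by central status can still be found by crossing the status listing with the duration-of-response listing; stable disease could only be inferred. That concerns which Part 2 listings are produced, not how 8.2 defines a population. Adding best response by central status would also sit poorly with the sponsor's decision to drop the concordance analysis for small numbers.

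**Conclusion.** No change to the plan follows. The Biomarker Population is a leftover definition, a clerical matter, and analysts following 8.4.5 as written will list all 9 treated Arm D participants. On that reading no rows are lost and no endpoint, denominator, estimate or conclusion moves. The primary ORR is unaffected on either reading. All treated participants is the right basis for it, because the 35% benchmark in 8.1.2 is for locally diagnosed patients.

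The expected loss of 2.25 rows, and the 92% chance of losing at least one, belong only to the strained reading. They assume the 25% planning rate and independence between participants.

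One thing cannot be checked. Sections 8.3.2.1 and 8.4.8 defer immunogenicity details to a statistical analysis plan, and no separate plan is part of the document reviewed. Such a plan could assign populations to listings. The conclusion rests on the protocol text alone.

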## **8.3 Endpoints**

### **8.3.1 Primary Endpoint(s)**

#### **8.3.1.1 Part 1**

The primary objective of Part 1 is to characterize the safety and tolerability of nivolumab plus ipilimumab in Chinese participants. The primary objective will be measured by:

- Number and percent of all treated participants that experience AEs occurring up to 100 days after the last dose of study drug (time frame - on a continuous basis up to 100 days after the last dose of study drug)
- Number and percent of all treated participants that experience SAEs occurring up to 100 days after the last dose of study drug (time frame - on a continuous basis up to 100 days after the last dose of study drug)
- Number and percent of all treated participants that experience AEs leading to discontinuation occurring up to 100 days after the last dose of study drug (time frame - on a continuous basis up to 100 days after the last dose of study drug)

- Number and percent of all treated participants that experience AEs leading to death occurring up to 100 days after the last dose of study drug (time frame - on a continuous basis up to 100 days after the last dose of study drug)
- Number and percent of participants with clinical laboratory abnormalities by worst toxicity grade by NCI CTCAE version 4.0 (as assessed at the planned times listed in [Table 5.1-1](#), [Table 5.1-2](#), [Table 5.1-3](#), [Table 5.1-4](#), [Table 5.1-5](#), [Table 5.1-6](#) and [Table 5.1-7](#)) (time frame - on a continuous basis up to 100 days after the last dose of study drug)

### **8.3.1.2 Part 2**

The primary objective of Part 2 will be measured by the primary endpoint of BICR-assessed ORR. It is defined as the number of participants with a BOR of confirmed CR or PR, according to RECIST 1.1 criteria, divided by the number of treated participants. The final analysis of the primary endpoint will occur at least 6 months after the last participant's first dose of study therapy. The BOR is defined as the best response designation recorded between the date of first dose and the date of initial objectively documented progression per RECIST 1.1 or the date of subsequent therapy, whichever occurs first. For participants without documented progression or subsequent therapy, all available response designations will contribute to the BOR determination. For purposes of analysis, if a participant receives one dose and discontinues the study without assessment or receives subsequent therapy prior to assessment, this participant will be counted in the denominator (as non-respondent).

The BICR-assessed ORR will be further characterized by rate of CR and PR.

### **8.3.2 Secondary Endpoint(s)**

#### **8.3.2.1 Part 1**

##### **Pharmacokinetics**

The Part 1 secondary objective of characterizing the PK of nivolumab and ipilimumab in Chinese participants will be measured by PK parameters derived from serum concentration versus time data by non-compartmental analysis method. Details of PK sample collection are provided in [Section 5.5](#). All individual PK parameters will be listed and summarized for each analyte, including any exclusions and reasons for exclusion from summaries. The PK parameters to be assessed for nivolumab and ipilimumab, if data permits, include

- Cmax - Maximum observed serum concentration
- Tmax - Time of maximum observed serum concentration
- AUC(0-T) - Area under the plasma concentration-time curve from time zero to the last time of the last quantifiable concentration.
- AUC(TAU) - Area under the concentration-time curve in one dosing interval
- Ceoinf - Serum concentration achieved at the end of study drug infusion
- Ctrough - Trough observed serum concentration at the end of dosing interval
- Ctau - Concentration at the end of dosing interval

- CLT - Total body clearance
- Css-avg - Average concentration over a dosing interval (AUC(TAU)/tau)
- AI - Accumulation index; ratio of an exposure measure at steady-state to that after the first dose (exposure measure includes AUC (TAU), Cmax, or Ctau).
- T-HALFeff - Effective elimination half-life that explains the degree of accumulation observed for a specific exposure measure (exposure measure includes AUC(TAU), Cmax, or Ctau)

The serum concentration may also be pooled with other datasets for population PK analysis, which will be presented in a separate report.

### **Immunogenicity**

The Part 1 secondary objective relating to immunogenicity will be measured by the ADA status both at the sample level and at the participant level, and Nab if data permits. At the sample level a sample is characterized as baseline ADA-positive and ADA- persistent positive or ADA-negative to each study drug. At the participant level, relevant ADA endpoints include proportion of participants with a baseline ADA-positive sample, and proportion of ADA- persistent positive participants for each study drug. Time points for collection are specified in [Table 5.5.1-1](#) and [Table 5.5.1-2](#). Additional details will be presented in the statistical analysis plan.

#### **8.3.2.2 Part 2**

The secondary endpoint for Part 2 will be measured by:

- Investigator-assessed ORR, defined as the proportion of all treated participants whose BOR is either confirmed complete response (CR) or confirmed partial response (PR).
- Investigator-assessed and BICR-assessed disease control rate (DCR), defined as the proportion of participants whose BOR is confirmed CR or confirmed PR or stable disease (SD) for at least 12 weeks.
- Investigator-assessed and BICR-assessed duration of response (DOR), defined as the time between the date of first confirmed response to the date of the first documented tumor progression (per RECIST 1.1), or death due to any cause, whichever occurs first
- Investigator-assessed and BICR-assessed progression-free survival (PFS), defined as the time from the first dosing date to the date of first objectively documented disease progression per RECIST 1.1 (ie, radiologic) or death due to any cause, whichever occurs first.

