##### **Part 2:**

- Investigator-assessed ORR: defined as the BOR of confirmed CR or PR, according to RECIST 1.1 criteria.
- Investigator- and BICR-assessed DCR defined as number of participants with a BOR of confirmed CR, PR, or SD lasting at least 12 weeks divided by the number of treated participants.

- Investigator-assessed and BICR-assessed progression-free survival (PFS), defined as the time from the first dosing date to the date of first objectively documented disease progression per RECIST 1.1 (ie, radiologic) or death due to any cause, whichever occurs first.

Exploratory endpoints:

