AE Assessment (including SAE Assessment)			x					
Should occur at every visit throughout the study.
 
All AEs (SAEs or non-serious AEs), including those associated with SARS-CoV-2 infection, must be collected continuously during the treatment period.

**Table 5.1-4: On-Treatment Procedural Outline (CA209672) - Part 2, Arm D: nivolumab 3 mg/kg + ipilimumab 1 mg/kg Q3W × 4, followed by nivolumab 240 mg Q2W**

Procedure	Cycles 1 to 2 Q3W (1 cycle = 6 wks)			Cycle 3+ Q2W (1 cycle = 6 wks)				Notes
	Day 1 a	Day 22 a	Day 42 a	Day 1 a	Day 15 a	Day 29 a	Day 42 a	
Review of Concomitant Medications	x							Should occur at every visit throughout the study.
Laboratory Tests								
Laboratory Tests	x	x		x	x	x		Within 72 hours prior to dosing. Include CBC w/differential and platelets; Full Chemistry Panel: LDH, AST, ALT, ALP, T.Bili, (Direct Bili if T.Bili > ULN), BUN (or serum urea level), creatinine, Ca+, Mg+, Na+, K+, Cl-, amylase, lipase, glucose, albumin, T.Protein  To be done within 72 hours prior to dosing and results must be reviewed prior to dosing. Screening labs are acceptable if performed within the previous 72 hours and results are available.
Thyroid function testing	x			x				TSH, (free T3, Free T4 if TSH not within normal limits).  To be done within 72 hours prior to dosing and results must be reviewed prior to dosing.
Pregnancy Test	x			x				Serum or urine pregnancy test (minimum sensitivity 25 IU/L or equivalent units of HCG) to be done at screening visit and within 24 hours prior to first dose and then every 4 weeks (± 1 week) regardless of dosing schedule.
Efficacy Assessments								
Tumor assessments b			x			x		The scans must be performed every 6 weeks (between Days 35 and 42 of the cycle) from date of first dosing for the first 24 weeks, and then every 12 weeks (between Days 35 and 42 of the cycle) thereafter (including treatment beyond progression) until initiation of subsequent anti-cancer treatment. This schedule should be followed even if treatment delay occurs.

**Table 5.1-4: On-Treatment Procedural Outline (CA209672) - Part 2, Arm D: nivolumab 3 mg/kg + ipilimumab 1 mg/kg Q3W × 4, followed by nivolumab 240 mg Q2W**

Procedure	Cycles 1 to 2 Q3W (1 cycle = 6 wks)			Cycle 3+ Q2W (1 cycle = 6 wks)				Notes

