EQ-5D-3L Questionnaire	x			x				Assessed prior to dosing every 6 weeks.  Questionnaires to be administered at the start of the clinic visit before the participant sees the physician and before any study-related procedures are done (with the exception of procedures completed 72 hours prior to visit). If a dose is delayed, the administration of the participant-reported outcome measures scheduled for that same time point should also be delayed to coincide with when that time point's dosing actually occurs.
Clinical Drug Supplies								
Nivolumab Administration	x	x		x	x	x		Those supplied by BMS or sourced by the investigator.
Ipilimumab Administration	x	x						Those supplied by BMS or sourced by the investigator.

a To be done ± 2 days of scheduled visit. Every effort should be made to schedule visits within the timeframe stated in the protocol. In the case that the visits cannot be within the timeframe stated in protocol then the treatment period study procedures can be performed ± 2 days of the scheduled visit.

b As of Protocol Amendment 07: Assessments necessary for monitoring safety will continue per protocol until the follow-up visit 2 or 100 days after study drug discontinuation, whichever occurs later. Collection of PK and immunogenicity data is not applicable. Analyses of PK and immunogenicity will be based on the samples analyzed before implementation of protocol amendment 07.

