## **5.4          *Efficacy Assessments***

### **5.4.1       *Imaging and Clinical Assessment***

Change in tumor measurements and tumor response will be assessed by investigators (Part 1) or by both BICR and investigators (Part 2) using the RECIST 1.1 criteria ([Appendix 1](#)).

Study evaluations will take place in accordance with [Table 5.1-1](#), [Table 5.1-2](#), [Table 5.1-3](#), [Table 5.1-4](#), [Table 5.1-5](#), [Table 5.1-6](#), and [Table 5.1-7](#).

Baseline assessments should be performed within 28 days before date of first dosing. Chest, abdomen, pelvis and any clinically indicated sites determined by the investigator should be assessed at baseline. Subsequent assessments should utilize the same imaging modality. For Part 1, tumor response should be evaluated every 6 weeks from date of first dosing for the first 24 weeks (between days 35 and 42 of the cycle), and then every 12 weeks (between days 35 and 42 of the cycle) thereafter until disease progression (including treatment beyond progression) or unacceptable toxicities. For Part 2, tumor response should be evaluated every 6 weeks (between days 35 and 42 of the cycle) from date of first dosing for the first 24 weeks and then every 12 weeks (between days 35 and 42 of the cycle) thereafter until initiation of subsequent anti-cancer treatment.

Tumor assessments for all participants should continue as per protocol even if dosing is delayed or discontinued. Changes in tumor measurements and tumor responses will be assessed by the same investigator per study design using RECIST 1.1 criteria. Investigators will also report the number and size of new lesions that appear while on study. The time point of tumor assessments will be reported on the eCRF based on the investigator's assessment using RECIST 1.1 criteria (See [Appendix 1](#)). Assessments of PR and CR must be confirmed at least 4 weeks (28 days) after initial response. A Best Overall Response of SD requires a minimum of 35 days on study from date of first dosing to the date of the first imaging assessment.

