#### **Secondary and Exploratory Endpoint Methods**

ORR based on Investigators' assessment will be summarized and further characterized by rate of CR and PR as above.

BICR-assessed and Investigator-assessed DCR will be summarized and corresponding two-sided exact 95% CI using the Clopper-Pearson method will be provided.

BICR-assessed and Investigator-assessed DOR will be listed for participants who achieve confirmed PR or CR.

PFS and OS will be listed.

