### 2.3.3 Best Overall Response

Best response determination of complete or partial response requires confirmation: Complete or partial responses may be claimed only if the criteria for each are met at a subsequent time point of  $\geq 4$  weeks (28 days) later. In this circumstance, the best overall response can be interpreted as in Table 2.3.3-1. When SD is believed to be best response, it must meet the protocol specified minimum time from the date of first treatment or randomization date.

For example, if the first scheduled follow-up imaging visit is Week 6 ( $\pm 7$  days) for a particular protocol, a Best Response of SD can only be made after the subject is on-study for a minimum of 6 weeks (42 days) minus 7 days, for an absolute minimum time on-study of 35 days from the reference start date (reference date is considered Day 1 on study). If the subject is not on-study for at least this amount of time, any tumor assessment indicating stable disease before this time period will have a Best Response of NE unless PD is identified.

**Special note on response assessment:** When nodal disease is included in the sum of target lesions and the nodes decrease to ‘normal’ size ( $< 10$  mm), they may still have a measurement reported on scans. This measurement should be recorded even though the nodes are normal in order not to overstate progression should it be based on increase in size of the nodes. As noted earlier, this means that patients with CR may not have a total sum of ‘zero’ on the case report form (CRF).

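### Part 2 DCR: does the unstated end of 12-week stable disease leave the result to the day of the Week 12 scan?

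*Combined protocol and SAP*

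**What the plan says.** Section 8.3.2.2 has DCR, by investigator and by BICR, "defined as the proportion of participants whose BOR is confirmed CR or confirmed PR or stable disease (SD) for at least 12 weeks". The Synopsis words the SD part and the denominator as "SD lasting at least 12 weeks divided by the number of treated participants". Section 8.4.2.2 gives one method for both assessors: "BICR-assessed and Investigator-assessed DCR will be summarized and corresponding two-sided exact 95% CI using the Clopper-Pearson method will be provided". No hypothesis, threshold or decision is attached to DCR.

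The scan schedule for Arm D is in Table 5.1-4: "The scans must be performed every 6 weeks (between Days 35 and 42 of the cycle) from date of first dosing". This spacing holds up to Week 24, and it is kept when dosing is delayed. Footnote a adds that "the treatment period study procedures can be performed ± 2 days of the scheduled visit".

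The only timing rule for SD concerns whether it may be assigned at all. Section 5.4.1 asks, for a best overall response (BOR) of SD, for "a minimum of 35 days on study from date of first dosing to the date of the first imaging assessment". Appendix 1, Section 2.3.3, shows in a generic example how 35 days arises from a Week 6 scan with a 7-day window, and counts the reference date as Day 1. Under Section 8.3.1.2, the BOR period closes at "the date of initial objectively documented progression per RECIST 1.1 or the date of subsequent therapy, whichever occurs first".

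In the same list as DCR, DOR and PFS each have a start and an end event (progression or death). The SD duration inside DCR has neither.

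**The concern.** The 12-week threshold falls on the last day of the Week 12 scan window, so most on-time scans come a few days before it. At Week 6 the protocol meets the same difficulty by setting the SD minimum at the early edge of the window (35 days rather than 42). It does not do so at Week 12, and it does not say whether SD runs to the last scan that shows it or to progression.

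Two programmers could therefore derive different DCR counts from the same on-schedule images. The participant at issue is an ordinary one: SD at Week 12, then progression at Week 18 or a new therapy. DCR is reported twice, each time with an exact interval, and in 9 participants a single reclassification is visible in the point estimate.

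**Working it through.** **Inputs.** Cycle length 6 weeks = 42 days, scans on Days 35 to 42 of the cycle, tolerance ±2 days (Table 5.1-4). SD minimum 35 days (Section 5.4.1; Appendix 1, Section 2.3.3). DCR threshold 12 weeks (Section 8.3.2.2). 9 treated participants (Sections 3.1.1 and 8.1.2).

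**The plan's own figure.** 6 × 7 − 7 = 35 days, which reproduces the stated minimum.

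**Week 12 window, first dose = Day 1.** From 42 + 35 = 77 to 42 + 42 = 84. With +2 days on the Day 42 visit the latest day is 86. If −2 days is also read onto the early edge, the earliest is 75. The threshold is 12 × 7 = 84 days.

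**Reading A: SD ends at the last SD scan, and that scan is the Week 12 scan.**

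| Day count | Days 77–84 that reach 84 days | Days 85–86 |
|---|---|---|
| Study day (first dose = Day 1) | Day 84 only (1 of 8) | both pass |
| Elapsed (study day − 1) | none (0 of 8) | both pass |

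**Reading B: SD ends at progression or death.** The Week 18 scan falls from 84 + 35 = Day 119 to 84 + 42 = Day 126. SD at Week 12 with progression first seen at Week 18 then lasts at least 119 − 1 = 118 elapsed days, above 84 for every Week 12 scan day. Among participants with an observed progression, scan day matters only when progression is first seen at the Week 12 scan itself: on the Day 1 count, a scan on Day 84 or later would credit 12 weeks and one on Days 77 to 83 would not.

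**Unaffected under either reading.** Confirmed CR or PR, and SD still present at the Week 18 scan (Day 119 or later).

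**Size.** One participant is 1/9 = 11.1 points. Clopper-Pearson 95% intervals: 6/9 = 66.7% (29.9 to 92.5, width 62.6 points) and 7/9 = 77.8% (40.0 to 97.2, width 57.2 points). The shift is less than a fifth of either width (11.1/57.2 = 0.19).

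**Carrying the 7-day allowance to Week 12.** 84 − 7 = 77 days, that is 77/7 = 11 weeks. On the Day 1 count all of Days 77 to 84 pass. On the elapsed count Day 77 still fails (76 days), and Days 75 and 76 fail on both.

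**Timing.** Enrollment closed on 20-Dec-2021. If the last first dose was no later than that date, Day 84 was no later than 13-Mar-2022, which is 162 days before Amendment 07 (22-Aug-2022).

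**The case for a change.** The best case for acting is that the omission is plain, the protocol already shows how to handle it at Week 6, and the remedy costs one sentence. Section 5.4.1 times SD to an imaging date, which points towards the last-scan reading, and on that reading an on-time scan usually fails the 12-week test. Timing SD to progression does not remove every difficulty either. It can credit disease control to someone whose progression is found at the Week 12 scan, and it needs a censoring rule for a participant who has no scan after Week 12.

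Much of this stands. The end event and the day count are not written, and whoever programs DCR must settle both, along with the censored case.

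Three parts do not carry. First, the rule in Section 5.4.1 decides whether SD may be assigned at the first scan; it does not say how SD duration ends. The last-scan reading is thus as much an inference as the progression reading, and the latter has the support of DOR and PFS in the same list. Second, nothing suggests that the two assessors would be derived differently: Sections 8.3.2.2 and 8.4.2.2 give one definition and one method for both. Third, a Day 77 threshold would not be a clarification. A plain 12-week threshold with no allowance is a legitimate choice, and accepting 11 weeks changes the endpoint. It would be set after the Week 12 scans were due and, against a last-scan rule at 84 days, could only raise DCR. Reporting both results would disclose that, but would add a second version of a descriptive figure in 9 participants.

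**Conclusion.** No change to the plan follows. The definition is incomplete, but analysts fill this kind of gap in the derivation specifications: SD starts at first dose, ends at a named event, is counted on a stated day convention, and is derived alike for BICR and investigator. Scan day decides the outcome only if SD is timed to its last scan with no later SD scan, or, under the progression reading, if progression is first seen at Week 12 or follow-up stops there.

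The possible effect is 11.1 points per affected participant, against exact intervals of 57.2 to 62.6 points at six or seven controlled participants. The number affected cannot be estimated from the documents and may be zero. The primary ORR is untouched, no test or decision rests on DCR, and PFS will be listed, so progression times can be seen beside it.

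This rests on DCR remaining descriptive and on the cohort staying at 9. The protocol refers to a separate statistical analysis plan (Sections 8.3.2.1 and 8.4.8, for immunogenicity) and to a BICR charter (Section 7). Neither is among the documents reviewed, and either may already fix the rule. The conclusion does not depend on that.
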